1.5. Exploratory Virologic Objective

To evaluate the efficacy of EIDD-2801 to clear SARS-CoV-2 RNA and infectious virus.

Exploratory Virologic Endpoints:

- 1. Achievement of undetectable (below the LOD of the assay) viral RNA titers by Day 5 in NP swabs
 - by infectivity assay
- 2. Time to clearance of infectious virus in NP swabs
 - by infectivity assay
- 3. Clearance of infectious virus by Day 3 and Day 5 in NP swabs
 - by infectivity assay
- 4. The number of acquired single-nucleotide polymorphisms in SARS-CoV-2 genomes by Day 5 or Day 11 in NP swabs
 - by viral sequencing

Version: 7.0

1.6. Exploratory Clinical Objective

To ascertain the role of EIDD-2801 in improvement of clinical symptoms and signs of EIDD-2801.

Exploratory Clinical Endpoints:

- 1. Days of hospitalization
- 2. Time until on room air without requirement for supplemental oxygen
- 3. Time to resolution of COVID-19 symptoms defined as:
 - Fevers OR
 - At least one of the following symptoms: cough, shortness of breath, respiratory rate ≥20, radiographic evidence of pneumonia OR
 - other clinical symptoms or signs that are not otherwise explained by comorbidities or codiagnoses
- 4. Number of days until a 2-point decrease in stage according to the WHO Ordinal Scale for Clinical Improvement (Appendix 1).
- 5. Radiologic improvement by grading chest diagnostics (when radiography is available)
- 6. Change in IL-6 levels by Day 5

1.7. Pharmacokinetic Objectives

The pharmacokinetic (PK) objectives will be assessed on dosing Days 3 and 4 in participants enrolled at clinical sites able to conduct the collections. These sites include but are not limited to

Secondary:

To evaluate EIDD-1931 PK in plasma in a subset of participants.

Exploratory:

To characterize the PK of EIDD-2061 (NHC-TP) in peripheral blood mononuclear cells (PBMC) in a subset of participants.

Pharmacokinetic Endpoints:

Secondary (plasma analysis):

- 1. Maximum EIDD-1931 concentration (C_{max})
- 2. 1.5-hour EIDD-1931 concentration (C_{1.5})
- 3. 3-hour EIDD-1931 concentration (C₃)
- 4. Area under the concentration: time curve of EIDD-1931 (AUC)
- 5. Elimination half-life (t_{1/2}) EIDD-1931

Version: 7.0

Version: 7.0 18 May 2021

Exploratory (PBMC analysis):

- 1. Maximum EIDD-2061 concentration (C_{max})
- 2. EIDD-2061 time of maximal concentration (t_{max})
- 3. Elimination half-life of EIDD-2061 (t_{1/2})
- 4. Area under the concentration: time curve of EIDD-2061 (AUC₀₋₁₂)
- 5. Parent: metabolite (EIDD-1931:EIDD-2061) concentration ratio at each time point, in which both plasma and PBMC are processed for PK analysis

2. BACKGROUND AND SCIENTIFIC RATIONALE

2.1. Abstract

SARS-CoV-2 has infected over 5 million people worldwide since December 2019, with >300,000 fatalities reported as of the date of this protocol (Johns Hopkins University Coronavirus Resource Center: https://coronavirus.jhu.edu/map.html). In this unprecedented global crisis, the medical community is lacking adequate tools to combat the severe outcomes of COVID-19: respiratory collapse, multi-system organ failure, and death. There is a desperate need for safe and effective antiviral therapies to mitigate the natural course of COVID-19, especially in those who are at high risk for severe disease. Currently, there are no approved therapeutics specific for COVID-19.

EIDD-2801 (also known as MK-4482) is an orally bioavailable prodrug of EIDD-1931, a small molecule ribonucleoside analogue that was developed for respiratory viruses. EIDD-2801 has demonstrated potent in vitro antiviral activity against a broad array of coronaviruses including SARS-CoV-2, Severe Acute Respiratory Syndrome Coronavirus (SARS-CoV), and Middle East Respiratory Syndrome-coronavirus (MERS-CoV), and it has shown in vivo activity in animal models of SARS-CoV and MERS-CoV (Agostini et al, 2019; Sheahan et al, 2020). EIDD-2801 is currently in Phase 1 clinical trials.

We propose a Phase 2a randomized, placebo-controlled, double-blinded clinical trial of EIDD-2801 in hospitalized men and women (aged 18+ years) with PCR-confirmed SARS-CoV-2 infection who also have evidence of symptomatic COVID-19. We plan to enroll hospitalized patients who present within 7 days of symptom onset for a 5-day course of twice daily (BID) dosing of EIDD-2801 or placebo. We will follow participants for every hospitalized day and after they are discharged, for 28 days after the first dose. The primary endpoint will be the achievement of undetectable (below the LOD of the assay) SARS-CoV-2 RNA in NP swabs by Day 5 (end-of-treatment). Secondary clinical endpoints will include the time until virologic clearance (by RNA testing), rate of decline in viral RNA, peak stage on the WHO Ordinal Scale for Clinical Improvement, requirement for additional antivirals, duration of ICU stay, duration of mechanical ventilation, or death. Safety outcomes will include AEs, SAEs, physical examination with vital signs, ECGs, and laboratory measurements (including CBC, CMP, and urinalysis). We will measure the PK of EIDD-1931, the primary circulating form of EIDD-2801, in plasma. We will also collect PBMCs for measurement of EIDD-2061 (NHC-TP), as an exploratory objective. PK sampling will be assessed on dosing days 3 and 4 in participants enrolled at clinical sites able to conduct the collections. These sites include but are not limited to

. We anticipate enrollment of 80 participants in this trial at the following dose levels: EIDD-2801 200 mg, EIDD-2801 400 mg, EIDD-2801 800 mg, and placebo. In the primary analysis, we will compare the proportion of participants in each EIDD-2801 and placebo groups who achieve virological clearance.

Version: 7.0

2.2. Background

COVID-19 is a disease caused by the SARS-CoV-2 that was first detected in China's Hubei province in December 2019. It is a systemic disease with influenza-like symptoms; a subset of patients with severe disease can experience respiratory decline, acute respiratory distress syndrome (ARDS), multi-system organ failure, and death. SARS-CoV-2 has infected over 5 million people worldwide since its emergence, with >300,000 fatalities reported as of the date of this study protocol (Johns Hopkins University Coronavirus Resource Center: https://coronavirus.jhu.edu/map.html).

There have been suggestions that the worst consequences of SARS-CoV-2 are seen in people with the highest viral burden (Wolfel et al. 2020). Although numerous agents are currently being tested in clinical trials, the majority of these are re-purposed drugs that are not specifically developed for SARS-CoV-2 or other coronaviruses. There is an urgent need for direct-acting SARS-CoV-2 antiviral agents that can be used in patients to mitigate the worst complications of the infection.

SARS-CoV-2 is an enveloped, positive-sense, single-strand RNA beta-coronavirus that is related to SARS-CoV and distantly to MERS-CoV. SARS-CoV-2 has a genome of ~30kb which comprises 4 structural proteins and 16 non-structural proteins. Among the non-structural proteins is nsp12, the RNA-dependent RNA polymerase (RdRp) that is required to replicate the viral genome. Many successful antivirals for other viruses target the RdRp: nucleos(t)ide inhibitors for Human Immunodeficiency Virus (HIV)-1 and hepatitis B, NS5B inhibitors for hepatitis C. However, many nucleoside analogues fail to inhibit coronaviruses because of the unique coronavirus 3'-5' exoribonuclease (nsp14) that confers proofreading activity to the CoV RdRp. Only 2 nucleoside analogues to date have been shown to overcome the coronavirus proofreading activity and inhibit a broad range of coronaviruses: remdesivir and EIDD-2801/EIDD-1931 (Agostini et al, 2018; Agostini et al, 2019).

EIDD-2801 (also known as MK-4482) is an oral prodrug of EIDD-1931 ([N4-HYDROXY-5'-O-(2-METHYLPROPANOYL)CYTIDINE, NHC], a novel small molecule ribonucleoside analogue with potent *in vitro* inhibition of a broad array of coronaviruses including SARS-CoV-2, SARS-CoV, and MERS-CoV (Sheahan et al, 2020). EIDD-2801 is converted into its circulating intermediate form, EIDD-1931, by non-specific esterases in plasma—this is the primary form found in systemic circulation. EIDD-1931 is then taken up by target mononuclear cells and enzymatically converted by host kinases to the metabolites 5'-monophosphate EIDD-1931 and 5'-triphosphate EIDD-1931 (also called EIDD-2061, or NHC-TP). The 5'-triphosphate form is a competitive antagonist of the RNA-dependent RNA polymerase (RdRp), while the 5'-monophosphate form promotes lethal mutagenesis in the nascent viral RNA strand, thus impacting downstream viral processes. EIDD-1931 has a median effective concentration (EC50) of 0.3 micromolar against SARS-CoV-2 *in vitro*, demonstrating a 1000-fold reduction in SARS-CoV-2 viral titers, as well as reduced lung hemorrhage and damage in a murine model of SARS-CoV.

Version: 7.0

Version: 7.0 18 May 2021

Pharmacologic aspects of EIDD-1931 and its metabolites have been evaluated in *in vitro* cell culture systems, as well as pre-clinical animal models. Anabolic PK assessments were characterized in cultured human bronchial tracheal epithelial cells. Following ex vivo incubation of epithelial cells with 20 μM EIDD-1931, there was rapid conversion to the EIDD-1931 metabolite (EIDD-Triphosphate, EIDD-TP) within the first 60 minutes. Plateau concentrations of EIDD-TP (4 nmol/10⁶ cells) were achieved within 4 hours and remained stable for 24 hours. Removal of drug led to persistence of the metabolite over a 24-hour period. The estimated intracellular half-life (t_{1/2}) of EIDD-TP was 4 hours. Comparable kinetics were observed in mouse lung tissue post-administration of an oral 500 mg/kg dose.

The orally bioavailable isopropylester compound, EIDD-2801, has been evaluated in an ongoing, Phase 1, randomized, double-blind, placebo-controlled single-ascending and multiple-ascending dose first inhuman study to assess its safety, tolerability, and PK. A total of 130 healthy participants (109 males and 21 females) received at least 1 dose of EIDD-2801 or placebo in the Phase 1 trial EIDD-2801-1001. Preliminary, unblinded safety data are available for all subjects. Review of these safety data indicates that single oral doses of up to 1600 mg EIDD-2801 or placebo and multiple oral doses of up to 800 mg EIDD-2801 or placebo Q12H for 5.5 days have been generally well tolerated in healthy participants. Further details are provided in Section 2.3.1.

The prodrug (EIDD-2801) was generally not detectable in plasma following single (50 to 1600 mg) or multiple doses (50 to 800 mg BID for 5.5 days) of MK-4482. Plasma concentrations of the nucleoside metabolite (EIDD-1931) were detectable. T_{max} occurred approximately 1 hour post dose. Plasma EIDD-1931 concentrations generally declined in a monophasic manner, with a $t_{1/2}$ of approximately 1 hour. A biphasic profile with a later, slower elimination phase (t_{1/2} ranging from 1.47 to 19.2 hours) was observed in some participants (following single doses of 1200 mg and 1600 mg and following multiple doses of 600 mg and 800 mg). C_{max} and AUC increased in an approximately dose-proportional manner across the range of doses tested. No accumulation occurred following multiple dosing (Q12H for 5.5 days), and administration in the fed state did not meaningfully impact plasma exposure of EIDD-1931. There were no significant detectable concentrations of EIDD-2801; initial PK parameters were identified for EIDD-1931 concentrations in plasma. Following multiple doses of 100 mg BID EIDD-2801 orally in the fasted state, median t_{max} was 1.25 hours post-dose (range 1-2 hours), and concentrations declined monophasically and were quantifiable until the 6 to 9-hour time points. The apparent terminal half-life (t_{1/2}) was 0.918 and 0.969 hours on Days 1 and 6, respectively. AUC_{tau} was 853 ng*h/mL (%CV 19.9), and C_{max} was 395 ng/mL (%CV 18.5). The increase in exposure between the 50 mg and 100 mg doses was slightly supraproportional with the 2-fold increase in dose resulting in a 2.23-fold increase in AUCtau and 2.31-fold increase in Cmax. (EIDD-2801 Investigator's Brochure, V3.0, 2020).

2.3. Known Potential Risks

2.3.1. Clinical Findings

EIDD-2801 has been studied in a single and multiple dose escalation study in humans that includes a food effect cohort. All subjects have completed participation in the study and preliminary data are available.

A total of 130 healthy volunteers were enrolled in this study. Sixty-four participants received a single dose between 50 and 1600 mg EIDD-2801 or placebo; 56 participants received multiple doses between 50 and 800 mg EIDD-2801 or placebo BID for 5.5 days; and 10 participants received a single dose of

200 mg EIDD-2801 in the fed state followed by a single dose of 200 mg EIDD-2801 in the fasted state after a washout period of 14 days, or vice versa.

Among participants who received single doses of EIDD-1801 or placebo, a greater proportion of participants reported AEs following administration of placebo (43.8%) than following administration of EIDD 2801 (35.4%). One moderate AE (headache) was reported by 1 participant following administration of EIDD-2801 at the 400-mg dose level, and 2 moderate AEs (nausea and headache) were reported by 1 participant following administration of placebo. No severe AEs were reported. The most frequently reported AE was headache, which was reported by 18.8% of participants who were administered placebo and 12.5% of participants who were administered EIDD-2801.

Among participants who received multiple ascending doses of EIDD-2801 or placebo BID over 5.5 days, a greater proportion reported AEs following administration of placebo (50.0%) than following administration of EIDD-2801 (42.9%). With the exception of 1 participant in the 200 mg BID group who reported moderate AEs of sore throat, aching limbs, and flu-like symptoms, all other AEs were mild in severity. The most frequently reported AE was diarrhea, which was reported by 7.1% of participants who were administered EIDD-2801 and 7.1% of participants who were administered placebo. One participant had an AE of mild, truncal, maculopapular, pruritic rash following multiple doses of 800-mg EIDD 2801, which was considered by the investigator to be related to the study drug; this AE resulted in early discontinuation of the study drug dosing on Day 3. The participant was administered a topical steroid and anti-histamines, and the AE resolved after 18 days.

Among participants in the food-effect evaluation, 3 participants reported 1 AE each, all of which were mild in severity.

There were no serious AEs reported in this study and there were no trends of increased frequency or severity of AEs with higher doses of EIDD-2801.

There were no clinically significant findings in clinical laboratory, vital signs, or ECG data.

(Section 2.3.2.2). However, no

clinically significant changes in hematological parameters were seen in the Phase 1 study.

2.3.2. Nonclinical Findings

2.3.2.1. Effects on the Gastrointestinal Tract

2.3.2.2.

Protocol EIDD-2801-2004

Version: 7.0

2.3.2.4.

2.3.2.5.

2.3.2.5.1.

2.3.2.5.2.

2.3.2.5.3.

2.3.3.

2.4. Known Potential Benefits

EIDD-2801 has been administered to COVID-19 patients in ongoing studies and the safety and tolerability of single and multiple ascending doses has been tested in healthy adult volunteers (See Section 2.3.1).

After oral delivery, EIDD-2801 is rapidly hydrolyzed by circulating esterases to produce high circulating (plasma) levels of EIDD-1931. In cell culture systems, EIDD-1931 has been shown to inhibit replication of multiple viral pathogens from multiple RNA virus families including pathogenic CoV (e.g., SARS-CoV-2, severe acute respiratory syndrome (SARS-CoV), and Middle East Respiratory Syndrome (MERS)), influenza viruses (seasonal, pandemic, and avian subtypes), respiratory syncytial virus (RSV), alphaviruses (e.g., Eastern equine encephalitis virus (EEEV), Venezuelan equine encephalitis virus (VEEV), and Chickungunya virus (CHKV)), Filoviruses (e.g., Ebola virus (EBOV), and Zika virus (ZIKV)). In addition, EIDD-2801 is active against orthopox viruses probably because orthopox viruses encode their own unique RNA polymerase. Antiviral activity has been verified in animal models of CoV (MERS- and SARS-CoV), influenza, RSV, VEEV, CHKV, and EBOV. The primary mechanism of action of EIDD-2801 is inhibition of viral RNA replication by incorporation of EIDD-1931 monophosphate metabolite into the viral RNA genome resulting in induction of viral error catastrophe.

2.4.1. Potential Benefits of Treatment

EIDD-2801 has demonstrated activity against SARS-CoV-2 in vitro, and SARS-CoV as well as MERS-CoV in vitro and in vivo. EIDD-2801 has shown efficacy against CoV in animal models. In mice, EIDD-2801 was active in both a prophylactic and therapeutic setting (Painter et al, 2019). When EIDD-2801 was administered up to 24 hours after infection with SARS-CoV or up to 12 hours after infection with MERS-CoV, a reduction in viral lung titers, protection from both lung hemorrhage and weight loss, and improvements in pulmonary function were seen, compared to vehicle-treated (control) animals.

Nonclinical findings suggest that it will be active against SARS-CoV-2. More information regarding nonclinical activity of EIDD-2801 can be found in the Investigators' Brochure.

Version: 7.0

2.4.2. Potential Benefits of Clinical Monitoring and Virologic Testing

Participants enrolled in the study will undergo close clinical and laboratory monitoring that could facilitate improved management of COVID-19 with associated benefit to the individual, their family, and the community at large.

Version: 7.0

3. PATIENT POPULATION

Adults aged 18 years or older who are hospitalized with a new diagnosis of COVID-19 with a duration of symptoms ≤7 days. Patients requiring admission to an intensive care unit for mechanical ventilation are not eligible. Persons with Low English Proficiency (LEP) and who are non-English Speakers may join.

3.1. Inclusion Criteria for Enrollment

Participants who meet all the following criteria will be eligible for study participation:

- 1. Has COVID-19 disease, defined by having one or more of the following new symptoms and signs (within 7 days):
 - Fevers OR
 - At least one of the following: cough, sore throat, shortness of breath, respiratory rate ≥ 20, radiographic evidence of pneumonia OR
 - Anosmia OR
 - other clinical symptoms or signs of COVID-19 that are not otherwise explained by comorbidities or co-diagnoses
- 2. PCR+ test for SARS-CoV-2 within 6 days prior to randomization.
- 3. Has new signs or symptoms of COVID-19 that began ≤7 days of anticipated first dose of study drug.
- 4. Persons \geq 18 years old.
- 5. Is an inpatient at the time of first dose.
- 6. Is willing and able to comply with all study procedures including providing informed consent firsthand or via a legally authorized representative, collection of virology samples, and any safety tests that are not included as part of standard of care (SOC).
- 7. Is willing and able to take oral medications and is anticipated to be able to take the full course of 5 days of study drug.

Pregnancy and Contraception:

Therefore, treatment with EIDD-2801 is contraindicated in women who are pregnant or nursing and in the male partners of women who are pregnant. Extreme care must be taken to avoid pregnancy during the study and for 4 days after completion of EIDD-2801 dosing in female participants and for 4 days after completion of EIDD-2801 dosing in female partners of male participants.

- 8. A female participant is eligible to participate if she is not pregnant or breastfeeding and at least one of the following conditions applies:
 - Is not a woman of childbearing potential (WOCBP)

OR

• Is a WOCBP and using a contraceptive method that is highly effective (a low user dependency method OR a user-dependent method in combination with a barrier method),

Version: 7.0

or be abstinent from heterosexual intercourse as their preferred and usual lifestyle (abstinent on a long-term and persistent basis), as described in Appendix 2 during the intervention period and for at least 4 days after the last dose of study intervention. The investigator should evaluate the potential for contraceptive method failure (ie, noncompliance, recently initiated) in relationship to the first dose of study intervention.

- A WOCBP must have a negative highly sensitive pregnancy test (serum test is required) within 24 hours before the first dose of study intervention.
- Additional requirements for pregnancy testing during and after study intervention are located in Section 4.4.
- The investigator is responsible for review of medical history, menstrual history, and recent sexual activity to decrease the risk for inclusion of a woman with an early undetected pregnancy.
- Contraceptive use by women should be consistent with local regulations regarding the methods of contraception for those participating in clinical studies.
- Given the elevated risk of venous thrombotic events in patients hospitalized with COVID-19 (Benson et al 2020; Spratt et al 2020), estrogen-containing contraceptives must not be started to fulfill the contraceptive requirement of this study at any time during participant's hospitalization. If contraceptives are interrupted as standard of care management of COVID-19 patients and resumed at a later time point, such as at hospital discharge, then abstinence must be practiced for the defined period of back-up contraception per the contraceptive product labeling. After this period, contraceptive use must adhere to Appendix 2.
- 9. Male participants are eligible to participate if they agree to the following during the intervention period and for at least 4 days after the last dose of study intervention:
 - Be abstinent from heterosexual intercourse as their preferred and usual lifestyle (abstinent on a long term and persistent basis) and agree to remain abstinent

OR

• Must agree to use contraception unless confirmed to be azoospermic (vasectomized or secondary to medical cause [Appendix 2]) as detailed below:

Agree to use a male condom plus partner use of an additional contraceptive method when having penile-vaginal intercourse with a WOCBP who is not currently pregnant. Note: Men with a pregnant or breastfeeding partner must agree to remain abstinent from penile-vaginal intercourse or use a male condom during each episode of penile-vaginal penetration.

• Contraceptive use by men should be consistent with local regulations regarding the methods of contraception for those participating in clinical studies.

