3.2. Exclusion Criteria for Enrollment

Participants who meet any of the following criteria will not be eligible for participation

- 1. Is anticipated to require ICU admission for mechanical ventilation within 24 hours of enrollment.
- 2. Requires more than 6 liters/minute of oxygen to maintain O₂ saturation above 95%.
- 3. Is not expected to survive longer than 24 hours.

Version: 7.0

- 4. Has a platelet count less than 100,000/μL, hemoglobin <9 g/dL, or has a disorder of the hematologic system including anemic disorder or other blood dyscrasia, cancer of the hematologic system, history of bone marrow transplant, or other significant hematologic disease.
- 5. Women who are pregnant or breastfeeding.
- 6. Is experiencing DAIDS AE grading scale grade 4 baseline medical conditions or laboratory abnormalities.
- 7. Has received a vaccine for COVID-19 prior to enrollment, or plans to receive a vaccine for COVID-19 before the end-of-study visit.
- 8. Has received an experimental antiviral treatment for COVID-19 prior to enrollment.
- 9. Has received convalescent plasma or other monoclonal antibodies prior to enrollment.
- 10. Is participating in another clinical study that involves pharmacologic intervention or has participated in another study within 30 days of 5 half-lives of the investigational agent (observational study participation is permitted).
- 11. In the opinion of the investigator, has end-organ disease as a result of relevant comorbidities: chronic kidney disease (reduced glomerular filtration rate [GFR] <30 mL/min by the Modification of Diet in Renal Disease (MDRD) study equation prior to COVID-19 symptom onset), decompensated chronic liver disease or cirrhosis, decompensated congestive heart failure, active peripheral vascular disease including active diabetic ulcers, chronic pulmonary disease prior to COVID-19 symptom onset requiring bilevel positive airway pressure (BiPAP) or >4 L/min supplemental oxygen at baseline; if using ≤4 L/min supplemental oxygen at baseline, consultation with and approval of the sponsor is required prior to enrollment.
- 12. Has a diagnosis of cancer that is not in remission. Noninvasive cancers, such as basal and squamous cell carcinoma or history of in situ tumors are allowed at the discretion of the investigator after discussion with the sponsor.
- 13. Has received an organ transplantation.
- 14. Has received a bone marrow transplantation.

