8.5.2. Serious Adverse Event

An SAE is an undesirable sign, symptom or medical condition which:

- Results in death
- Is life threatening (defined as an event in which the participant was at risk of death at the time of the event; it does not refer to an event which hypothetically might have caused death if it were more severe)
- Requires inpatient hospitalization or causes prolongation of existing hospitalization (see note below for exceptions)
- Results in persistent or significant disability/incapacity
- Is a congenital anomaly/birth defect (note: reports of congenital anomalies/birth defects must also be reported on the Pregnancy Supplemental Form, although participants must have a negative pregnancy test prior to therapy and use at least 2 forms of non-hormonal contraception. All participants (men and women) must state that they will use 2 forms of contraception during the study and for 4 days after completion of EIDD-2801 dosing in female participants and for 4 days after completion of EIDD-2801 dosing in female partners of male participants.
- Is an important medical event (defined as a medical event(s) that may not be immediately life-threatening or result in death or hospitalization but, based upon appropriate medical and scientific judgment, may jeopardize the participant or may require intervention [e.g., medical, surgical] to prevent one of the other serious outcomes listed in the definition above.). Examples of such events include, but are not limited to, intensive treatment in an emergency room or at home for allergic bronchospasm; blood dyscrasias or convulsions that do not result in hospitalization.)

Events **not** considered to be SAEs are hospitalizations for the:

- Admissions as per protocol for a planned medical/surgical procedure or to facilitate a procedure.
- Routine health assessment requiring admission for baseline/trending of health status (e.g., routine colonoscopy).
- Medical/surgical admission for purpose other than remedying ill health state and was
 planned prior to entry into the study. Appropriate documentation is required in these
 cases.
- Admission encountered for another life circumstance that carries no bearing on health status and requires no medical/surgical intervention (e.g., lack of housing, economic inadequacy, care-giver respite, family circumstances, administrative).

Version: 7.0

- Version: 7.0 18 May 2021
- Escalation of care that is considered part of the disease progression of COVID-19

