Appendix 2. Contraceptive Guidance

Definition of Women of Childbearing Potential (WOCBP)

A woman is considered fertile following menarche and until becoming postmenopausal unless permanently sterile (see below):

If fertility is unclear (eg, amenorrhea in adolescents or athletes) and a menstrual cycle cannot be confirmed before first dose of study intervention, additional evaluation should be considered.

Women in the following categories are not considered WOCBP:

- Premenarchal
- Premenopausal female with 1 of the following:
 - Documented hysterectomy
 - Documented bilateral salpingectomy
 - Documented bilateral oophorectomy

For individuals with permanent infertility due to an alternate medical cause other than the above (eg, Mullerian agenesis, androgen insensitivity), investigator discretion should be applied to determining study entry.

Note: Documentation can come from the site personnel's review of the participant's medical records, medical examination, or medical history interview.

Postmenopausal female

A postmenopausal state is defined as no menses for 12 months without an alternative medical cause.

A high follicle stimulating hormone (FSH) level in the postmenopausal range may be used to confirm a postmenopausal state in women not using hormonal contraception or hormone replacement therapy (HRT). However, in the absence of 12 months of amenorrhea, confirmation with two FSH measurements in the postmenopausal range is required.

Females on HRT and whose menopausal status is in doubt will be required to use one of the nonhormonal highly effective contraception methods if they wish to continue their HRT during the study. Otherwise, they must discontinue HRT to allow confirmation of postmenopausal status before study enrollment.

Version: 7.0 18 May 2021

Contraception Requirements

CONTRACEPTIVES ALLOWED DURING THE STUDY INCLUDE^a:

Highly Effective Methods That Have Low User Dependency

Failure rate of <1% per year when used consistently and correctly.

- Progesterone-only subdermal contraceptive implant^b
- Intrauterine hormone-releasing system (IUS)^c
- Non-hormonal intrauterine device (IUD)
- Bilateral tubal occlusion
- Azoospermic partner (vasectomized or secondary to a medical cause)

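### Section 3.1 contraindicates EIDD-2801 in men with a pregnant partner, yet inclusion criterion 9 admits them and no exclusion bars them; the contraception text in Section 8.5.2 also disagrees with criterion 8 and Appendix 2

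*Protocol*

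**What the plan says.** **Men with a pregnant partner.** The unnumbered lead-in to inclusion criteria 8 and 9 (protocol Section 3.1) says that "treatment with EIDD-2801 is contraindicated in women who are pregnant or nursing and in the male partners of women who are pregnant". It attaches no condition to this.

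Criterion 9 then lists what male participants must agree to in order to be eligible, during the intervention period and for at least 4 days after the last dose. For a man whose partner could conceive and is not pregnant, the requirement is "Agree to use a male condom plus partner use of an additional contraceptive method". The note that follows deals with the other case: "Men with a pregnant or breastfeeding partner must agree to remain abstinent from penile-vaginal intercourse or use a male condom during each episode" of penile-vaginal intercourse.

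In Section 3.2 the only exclusion that mentions pregnancy is number 5: "Women who are pregnant or breastfeeding".

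**Contraceptive methods.** Criterion 8 asks women of childbearing potential for "a low user dependency method OR a user-dependent method in combination with a barrier method", or long-term abstinence, and asks no contraception of women who cannot conceive. Appendix 2 lists the accepted methods, some of them hormonal, for example "Progesterone-only subdermal contraceptive implant".

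The congenital-anomaly bullet of the serious adverse event definition (Section 8.5.2) contains two further requirements. One says that "participants must have a negative pregnancy test prior to therapy and use at least 2 forms of non-hormonal contraception". The next says "All participants (men and women) must state that they will use 2 forms of contraception during the study" and for 4 days after dosing.

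**The concern.** A contraindication tells the site not to treat. The criterion 9 note tells the site to treat with a precaution. Both apply to the same men, and the protocol does not say which prevails. A site that screens from the numbered criteria can dose a man whom the lead-in says must not receive the drug. A site that follows the lead-in turns him away. Either decision could later be recorded as a deviation.

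The subject is embryo-fetal exposure, on which the protocol itself asks for great care, and the trial may run at up to seven sites (two named plus up to five more).

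The sentences in Section 8.5.2 add a second instruction on contraception that differs from the one used for enrolment. Staff who counsel participants from that section would ask for something other than criterion 8 and Appendix 2 require.

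**Working it through.** The plan gives no figure on this point. The check is a comparison of texts, followed by a count of the methods in Appendix 2.

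**1. Men with a pregnant partner**

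| Place | Status of these men |
|---|---|
| Section 3.1, lead-in | Contraindicated, no condition stated |
| Section 3.1, criterion 9 note | May enrol on abstinence or condom use |
| Section 3.2, exclusion 5 | Not mentioned (women only) |
| Section 3.2, exclusion 16 | Not named; investigator's judgement of risk to the participant |
| Section 3.2, the other 20 exclusions | Not mentioned |

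The note is part of an eligibility condition. Saying what these men must agree to presupposes that they may take part. For women, the lead-in's contraindication is enforced twice, by criterion 8 and exclusion 5. For men it is enforced nowhere. Exclusion 16 does not fill the gap, because the hazard here is to the partner's pregnancy and not to the participant.

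**2. Section 8.5.2 against criterion 8 and Appendix 2**

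Let S1 be the sentence requiring at least 2 non-hormonal forms, and S2 the sentence requiring 2 forms from all men and women.

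- Low-user-dependency methods in Appendix 2: implant, hormone-releasing intrauterine system, non-hormonal intrauterine device, tubal occlusion, azoospermic partner. That is 5.
- User-dependent hormonal methods: 4 combined (oral, intravaginal, transdermal, injectable) and 2 progestogen-only (oral, injectable). 4 + 2 = 6.

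| Accepted regimen | Forms | Non-hormonal forms | S1 | S2 |
|---|---|---|---|---|
| Implant or intrauterine system alone (2 of 5) | 1 | 0 | not met | not met |
| Other low-user-dependency method alone (3 of 5) | 1 | 1 | not met | not met |
| Hormonal method + one barrier (6 of 6) | 1 + 1 = 2 | 1 | not met | met |
| Hormonal method + double barrier | 1 + 2 = 3 | 2 | met | met |
| Criterion 9: condom + partner's method | 2 | depends on the partner's method | – | met |
| Abstinence | accepted in place of contraception | – | not met | not met |

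The smallest regimens that criterion 8 accepts therefore fail at least one of the two sentences. Some larger regimens satisfy both, so the mismatch is partial. The 4-day period after dosing is the same in Sections 3.1 and 8.5.2; the disagreement concerns which methods are needed, how many, and by whom.

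**The case against.** The best case for leaving this alone has five parts.

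- **Numbered criteria govern.** Section 3.1 makes eligibility depend on meeting the listed criteria. The lead-in is unnumbered, and criterion 9 addresses these men specifically, so a site working from the list has one usable instruction. This lessens the ambiguity. It does not remove it, because the lead-in is an unqualified safety statement in the same section and no order of precedence is given.
- **The risk is already managed.** Men admitted under the note must abstain or use a condom throughout dosing and for at least 4 days afterwards. Dosing lasts 5 days, and pregnancies in partners are reported and followed (Section 8.10.4). This stands, and it limits the seriousness of the point.
- **The rationale is not visible.** The lead-in opens as the conclusion of an argument that the public version does not show. This also stands in part: the protocol cannot tell us which statement is the wrong one. But both rules are legible, and a hidden rationale would not reconcile them.
- **The note might cover only breastfeeding partners and pregnancies discovered after enrolment.** This is a strained reading. The note names pregnant partners and is framed as something to agree to in order to be eligible.
- **Section 8.5.2 is leftover text.** Sites do not enrol from a definition of serious adverse events, and the method counts measure no participants and no risk. Agreed: this part is secondary, and the counts show only how far the wordings diverge. The sentences are nevertheless worded as obligations on participants.

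**Conclusion.** The concern holds. For any man whose partner is currently pregnant, Section 3.1 says both that he must not be treated and that he may be, and no exclusion settles it. How many such men would present cannot be worked out from the protocol.

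The mismatch in Section 8.5.2 is real but lesser: 5 of 5 low-user-dependency methods, each accepted alone, supply one form where two are asked for, and 6 of 6 hormonal methods with a single barrier supply one non-hormonal form where two are asked for.

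The possible consequence is uneven eligibility decisions and uneven embryo-fetal precautions between sites. The protocol does not show that any man would be dosed without a precaution. Alpha, power and the primary analysis are not affected. Nor is the Per Protocol Set, since Section 6.2.1 reserves complete exclusion from it for important deviations with a major effect on efficacy.

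The conclusion rests on the current wording alone and takes no view on which rule is toxicologically right. It should be fixed, because it concerns an operative eligibility and safety rule.

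**What to change.** Settle on one rule for men with a pregnant partner:

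- **Exclude them.** Add a numbered exclusion for men whose partner is currently pregnant, and delete the reference to pregnant partners from the criterion 9 note, keeping the part on breastfeeding partners; or
- **Admit them with precautions**, if the sponsor's reproductive-toxicity position supports this. Reword the lead-in so that the contraindication covers only women who are pregnant or nursing, and state there the abstinence-or-condom condition for men with a pregnant partner.

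In Section 8.5.2, replace both contraception sentences with a cross-reference to criteria 8 and 9 and Appendix 2. Check that the consent form states the same rule; its pages are not in the public document, so no mismatch there is presumed.

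The cost is a wording amendment and the consent check, with no new procedures. Only the first option touches accrual, and only for men with a currently pregnant partner.
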